SECTION III: STUDY PROTOCOL

1. **Study Abstract:** Provide a brief, non-technical summary of the study, including study purpose and methods.

The purpose of this investigation is to examine the evidence on emotion, language, and music, and propose a first step, in the form of a single-subject research design, to determine the most effective and efficient method for application to the rehabilitation of patients with aphasia. A single-subject adapted alternating treatment design will be used to compare two music conditions, using music with sung lyrics simultaneously with silent reading of the lyrics, and priming with music and sung lyrics followed by reading of the lyrics, with a control condition using reading materials without music. Risks are expected to be minimal. The risk is confidentiality. Risk management procedures in this study include: assuring confidentiality of participants, assuring qualified personnel, assuring convenient location, ensuring adequate enrollment, continual monitoring, addressing potential conflicts of interest, and making a plan to manage problems. Continual monitoring will be used to assess whether study interventions appear to be interfering with normal speech therapy treatment. If the researcher sees any signs of interference, the subject will be withdrawn from the research and study interventions will be stopped.

2. **Background:** Summarize background information about the research question(s.) Tell why the research is needed and include the relevance of this research to the contribution of this field of study. Also, provide references to relevant articles in the literature. (If you have more than 10 references, please submit the list of references as a separate attachment. Otherwise, please insert them here.)

Aphasia is a language disorder:

- Caused by left cortical lesions;
- Impacts all modalities of language including comprehension, expression, reading, and writing;
- And affects language processing from single words through higher levels of semantic and syntactic processing.
- Reading has been used effectively to improve language comprehension in patients with aphasia (Helm-Estabrooks, Albert, & Nicholas, 2014).

Emotional words facilitate language in individuals with aphasia (Landis, 2006; Landis, Graves, & Goodglass, 1982):

- Driven by activation of the amygdala;
- Amygdala activation enhances memory for emotional scenes/pictures (Canli et al., 2000).

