- Lesions in the amygdala negate the emotional word response (Vuilleumier et al., 2004).
- The amygdala also responded to nonlinguistic vocalizations (Fecteau, Belin, Joanette, & Armony, 2007).
- The emotional word effect crosses languages (Herbert et al., 2009).
- Labeling reduced amygdala activation and decreased affective response (Lieberman et al., 2007).
- The emotional word effect has not been demonstrated beyond the word level.

Music also evokes emotion and activates the amygdala (Blood & Zatorre, 2001).

- Brain regions involved in music processing are mainly supplied by the middle cerebral artery (MCA) bilaterally (Ayotte et al., 2000).
- Intensely emotional music activated brain structures involved in reward/motivation, emotion, and arousal (Blood & Zatorre, 2001).
- Musical aspects of language provide scaffolding for later development of the semantic and syntactic aspects of language (Brandt et al., 2012).

Music has been used for rehabilitation of patients with neurological impairments.

- The amygdala and visual extrastriate areas are intact in many patients with aphasia.

- Listening to music with lyrics was more effective than listening to language for improving language recovery in patients with aphasia in the early recovery period after stroke (Sarkamo et al., 2008).

In the Sarkamo et al. (2008) study, sixty-three percent of the music used contained lyrics.

- Linguistic meaning is accentuated when lyrics are embedded in music, and repeated exposure to songs increased ratings of meaningfulness of the lyrics (Thompson & Russo, 2004).
- Verbal material presented as song lyrics was learned and retrieved more efficiently than material presented verbally (Thaut et al., 2005).
- Listening to music, especially with lyrics, activated a more widely and bilaterally distributed network than listening to verbal material alone (Callan et al., 2006).
- Patients with aphasia repeat and recall more words from novel songs when singing than speaking along with a model (Racette et al., 2006).

Reading was not stimulated in the Sarkamo et al. (2008) study.

- Training more complex language can result in generalization to less complex, untrained language (Kiran & Thompson, 2003; Thompson, Shapiro, Kiran, & Sobecks, 2003).
- Reading is a more complex language activity than listening (Berl et al., 2011).
- Musical training transferred to improved speech and language in children, including reading (Moreno et al., 2008).

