Purpose: The purpose of this study is to translate neuroscience on emotion, music, and cognition into application for rehabilitation of aphasia, and test the effectiveness and efficiency of a new treatment, using listening to music with lyrics, combined with silent reading of the lyrics, to evoke emotion, engage the amygdala-extrastriate cortical projections, and increase arousal and attention to the reading material, to promote recovery of reading and retention of phrase-level reading material in patients with aphasia.

Significance: The impact of this study is anticipated to be a demonstration of increased effectiveness and efficiency of therapy directed toward recovery of language including reading comprehension in participants with aphasia. In addition, new material will be developed to increase options for treatment. Further, it will provide behavioral evidence to support hypotheses of either independent or shared neural pathways for processing musical and linguistic semantic meaning.

3. **Objectives:** State the research hypothesis or the question that the research will answer. List the research objectives and expected outcomes. **A primary outcome or objective must be identified.** After the statement of the primary objective, secondary objectives may be listed. Objectives should be simple and specific.

Primary objective: test the effectiveness and efficiency of a new treatment, using listening to music with lyrics, combined with silent reading of the lyrics, to promote recovery of reading and retention of phrase-level reading material in participants with aphasia.

Research questions:

1. Is music with lyrics (songs) presented simultaneously with written lyrics effective for facilitating recovery of reading of phrase-level material for participants with aphasia (independent processing)?
2. Is music with lyrics followed by presentation of the written lyrics effective for facilitating recovery of reading of phrase-level material for participants with aphasia (shared processing)?
3. Which procedure, simultaneous presentation or priming with the music/lyrics, is more effective for facilitating recovery of reading of phrase-level material for participants with aphasia?
4. Is one method more efficient for facilitating recovery of reading of phrase-level material for participants with aphasia?
5. Does one procedure result in greater retention of the trained material?

Research Hypotheses:

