1. Music with lyrics (songs) presented simultaneously with written lyrics will be effective for facilitating recovery of reading of phrase-level material for participants with aphasia.
2. Music with lyrics followed by presentation of the written lyrics will also be effective for facilitating recovery of reading of phrase-level material for participants with aphasia.
3. Simultaneous presentation will be more effective than priming with the music/lyrics for facilitating recovery of reading of phrase-level material for participants with aphasia.
4. Simultaneous presentation will be more efficient for facilitating recovery of reading of phrase-level material for participants with aphasia.
5. Simultaneous presentation will result in greater retention of the trained material.

4. **Study Design:** Give a description of the research design including use of placebo, randomization and an explanation of what is experimental. Include type of study: descriptive, retrospective, cross-sectional, longitudinal, prospective observational, pilot, experimental (controlled or non-controlled) or pilot.

This investigation uses a single-subject, adapted alternating research design to compare two different experimental conditions using music with lyrics combined with visual stimulation of the written lyrics, to extend the emotional word effect to phrases, in order to stimulate reading comprehension of the trained material for patients with aphasia. The two music conditions include 1) music with sung lyrics simultaneously with silent reading of the written lyrics; and 2) music with sung lyrics, followed by silent reading of the written lyrics (i.e. priming with the music). A control set without music will be used additionally within every third session to detect potential history and maturation effects. All conditions will be followed by a silent reading phrase-completion task composed of written words from the total combined sets of stimuli.

5. **Study Population:** Describe the subject population, including age, gender, ethnic characteristics and health status. State the inclusion/exclusion criteria along with how this was determined, and by whom. Please state whether pregnant women, children, or other vulnerable groups will be included or excluded. Provide rationale for using or excluding special populations. State the number of subjects or subject records necessary to complete the research.

Considerations in Participant Selection

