Seventh Step--Intervention phase (B) (see flowchart attached), each song (music with lyrics) from set 1 (B1 songs #1-10) will be played in its entirety. When the targeted verse or chorus plays, the written lyrics will be simultaneously shown along with the song lyrics. The ST will point to the words of the targeted verse/chorus which will be silently observed by the participant as they are sung. This will be repeated for all 10 songs. The phrase completion task will then be presented, including the ten phrases from the songs played that day and the five control phrases, without music. The participant will silently or orally read the phrase and orally read and/or circle or point to the phrase completion choice. Correct responses will be verbally reinforced. The next session, each song (music with lyrics) from set 2 (B2 songs #11-20) will be played in its entirety. After the song plays, the written lyrics from the targeted verse or chorus will be presented. The ST will point to the words of the targeted verse/chorus which will be silently observed by the participant. This will be repeated for all 10 songs. The phrase completion task will then be presented, including the ten phrases played that day and the five control phrases. The participant will silently or orally read the phrase and orally read and/or circle or point to the phrase completion choice. Correct responses will be verbally reinforced. This will be repeated for all 10 songs. For all interventions, the number of correct responses will be tallied on a LaPoint Base 10 form and the percent correct will be entered on the graph for that day. The same procedures will be repeated, alternating procedures on sets 1 and 2 on subsequent treatment visits, until a criterion of 9/10 (90%) x 3 consecutive visits is reached on both sets. If the criterion is not reached on one of the intervention sets, defined as no increase in percentage correct x 3 consecutive visits, a correction procedure will be applied using modeling of the correct response. If the criterion still is not reached, that intervention will be determined to be limited in effectiveness and discontinued. Every third session will be videotaped for a reliability check by the recruiter/research team member. When both of the sets (B1 and B2) have been acquired or one acquired and the other discontinued, the number of sessions to criterion will be counted for each intervention. (Expect length of time 2- 12 weeks)

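### The control phrases are tested right after ten full songs but have a music-free baseline, so a rise in the control cannot be read as history or maturation

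*Combined protocol and SAP*

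**What the plan says.** Section 4 (Study Design) gives the control one task: "A control set without music will be used additionally within every third session to detect potential history and maturation effects". The Study Abstract describes it as "with a control condition using reading materials without music".

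Section 6, Seventh Step, sets the order within a session. Each of the ten songs of the day's set "will be played in its entirety", with the lyrics shown during the song (set 1) or after it (set 2). In set 1 sessions one completion task follows, "including the ten phrases from the songs played that day and the five control phrases, without music". Set 2 sessions have the same order: "The phrase completion task will then be presented, including the ten phrases played that day and the five control phrases".

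The Sixth Step (baseline) tests all 30 phrases with the same type of task and describes no music. The Ninth Step retests the 30 phrases at three weeks, again with no music described.

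On mechanism, the Purpose paragraph in section 2 says the treatment is meant to evoke emotion and "increase arousal and attention to the reading material". The Background cites evidence that "Intensely emotional music activated brain structures involved in reward/motivation, emotion, and arousal".

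Section 8 analyses percent correct by phase, using celeration and split-middle lines, the binomial test, the two-standard-deviation band and statistical process control. It compares the control with the two music conditions for sessions to mastery, three-week retention and generalization.

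**The concern.** The control phrases are free of music only in the sense that no song is paired with them. When the participant answers them, ten songs have just been played. Arousal and attention are states of the participant, and need not stop at the ten phrases whose lyrics were shown. If the hypothesised mechanism works and spreads this way, control scores would rise from the first intervention visit, because that is when songs are first heard before the task.

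The control is there "to detect potential history and maturation effects". A rise could come from those sources or from the songs, and the plan gives no rule for telling them apart. At stake is how research questions 1 and 2 are answered, that is, whether each music procedure is effective at all. An investigator who sees the control rise may discount a music effect that is partly real.

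**Working it through.** The plan states no effect size, SD or power for this point, so there is no figure to reproduce. The check is algebra on the described test conditions, followed by illustrations under assumed values.

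**Components.** Let m be history and maturation (including practice), g any general effect of having just heard the songs, and d the effect specific to the phrases sung and shown. Effects are assumed additive, in percentage points.

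**Order as written** (baseline without songs; all phrases tested after songs in the intervention phase):
- change in control = m + g
- change in a music set = m + g + d
- music minus control = d

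The control's own change does not separate m from g. The music set's change from its own baseline still contains g + d. The direct contrast keeps only d.

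**Simultaneous versus priming.** Both session types play ten songs before the task, so g enters both sets. This ordering alone gives no reason to expect bias between them.

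**Illustration of the contrast.** Assume m = 0 and a total music gain T = g + d. Then control rise = g and contrast = T − g.

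| Share of T that is general | T = 40: control rise | T = 40: contrast | T = 20: control rise | T = 20: contrast |
|---|---|---|---|---|
| 0% | 0 | 40 | 0 | 20 |
| 25% | 10 | 30 | 5 | 15 |
| 50% | 20 | 20 | 10 | 10 |
| 75% | 30 | 10 | 15 | 5 |
| 100% | 40 | 0 | 20 | 0 |

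**How often the control would look raised with m = 0** (simulation, all inputs assumed):
- *Mean rise of at least 10 points.* Baseline accuracy 40%, five control items, 5 baseline and 12 intervention probes. This occurs in about 20% of participants with g = 0, 51% with g = 10 and 81% with g = 20. With only 4 intervention probes, closer to one session in three, it is about 26% with g = 0 and 77% with g = 20.
- *Two-standard-deviation band.* Baseline accuracy 30–50%, ten control items at 5 baseline visits, five items at 12 intervention probes, flagged when two consecutive points lie above the baseline mean plus 2 SD. This occurs in 19–20% of participants with no lift, 39–43% with 10 points, 60–66% with 20 and 79–84% with 30.

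The rates at g = 0 are noise from a short series with few items. Only the excess over them is due to the songs.

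**Order with control phrases before the first song, in both phases:**
- change in control = m (no same-session music in either phase)
- change in a music set = m + g + d − f, where f is any extra fatigue or time-in-session effect on phrases tested after the songs
- music minus control = g + d − f

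The control's own change now answers the history and maturation question. The direct contrast gains g but also takes on f.

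**Two inputs on which the text conflicts.** Section 4 puts the control within every third session, whereas the Seventh Step includes it in the described sessions of both types. Thirty phrases less two sets of ten leaves 30 − 20 = 10 control phrases, whereas the Seventh Step speaks of five. Under either frequency the control sits inside a music session, so the point does not depend on which is meant.

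**The case against.** The strongest reply is that little in the written analysis subtracts the control. Daily percent correct is analysed within each series by phase, and a music set's change from its own baseline keeps any general effect. The control comparisons in section 8 concern mastery, retention and generalization, and the retention test has no songs described. This stands. A reader might infer that a real music effect is understated throughout the analysis, or that a purely general effect would vanish. The documents support that only for a direct intervention-phase contrast of music with control.

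A reader might also infer that the control cannot serve its purpose at all. That goes too far. Control phrases tested in the same task share outside events, spontaneous recovery and practice with the music phrases, and a control that stays flat argues against history and maturation. What fails is the reading of a rise.

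It can further be said that the protocol links arousal to the reading material shown with the songs and does not claim that the lift spreads to other phrases; that the objective concerns trained material; and that a state effect would appear as a step at phase change and be absent at the retest, whereas maturation would show as slope. The first two make the size of g uncertain and may make d the quantity of most interest. They do not make a rising control interpretable. The third offers a hint, but the plan does not say how it would be used.

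Finally, testing the control first puts ten songs between the two groups of phrases in the intervention phase but not at baseline, so f is not fully matched. This also stands. It bears mainly on a daily music-minus-control difference that the plan does not specify. The flowchart and attachments are not visible, and item order within the task is unknown.

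**Conclusion.** The point holds in a limited form. The control's test conditions change from no music described to directly after ten songs at the phase boundary, so a rising control cannot be attributed to history or maturation as opposed to a general effect of the songs. This matters for the reading of research questions 1 and 2, and for any direct intervention-phase comparison of control with music, which would show only d. It does not by itself bias questions 3 to 5 or each music set's own baseline-to-intervention comparison.

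The size is unknown, because the documents give no effect sizes. The tabulated and simulated figures rest on additive effects, no maturation, and assumed accuracies, gains and numbers of probes; they show the mechanism only. If no general effect exists, nothing is lost. The change is still worth making before data are collected, because the visible plan has no way to separate m from g afterwards.

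**What to change.** 1. In the Seventh Step, in every session where the control is probed, give the control phrases before the first song and the ten music phrases after the songs.
2. In the Sixth Step, give the control phrases first as well, so that the control series is tested in the same position and without same-session music in both phases.
3. In section 8, state that history and maturation are judged from the control's own baseline-to-intervention change. State also that any direct music-minus-control difference then includes general arousal and time-in-session effects as well as item-specific learning.
4. Reconcile the control's frequency (section 4 against the Seventh Step) and its number of phrases (ten by subtraction against five).

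The cost is a few sentences and a reordered task sheet, with no added visits, items or participants. The completion task is given in two parts, though answer choices can still be drawn from the combined sets. The small downside is the unmatched time in session, which item 3 discloses.

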Eighth Step--Posttest BDAE-3 full version Reading subtests (extended posttest). (Expected length of time one visit)

Ninth Step--Retest retention of 30 phrases 3-week follow-up. (Expected length of time one visit)

Total number of visits: 16-48; total length of time 10-20 weeks per patient.

For CFMH or Roanoke Day Rehab, the PI, who is also the treating SLP, will make clear to subjects each time when standard therapy has ended and a research study intervention is about to begin. The subjects will be told approximately how long the research intervention is expected to take. For CRMH Inpatients, research will be separated in time and completed by a different SLP (the PI).

7. **Data Collection:** Attach a copy of your data collection tool or spreadsheet listing exactly what data is to be gathered during this research study. Describe below the data collection methods and how data be compiled for assessment.

Outcome Measures and Time Points

Pretest/post-test information on the ICF Body Functions/Structures, Activities, and Participation will be provided (Hurkmans et al. 2011).

The Boston Diagnostic Aphasia Examination (BDAE) (Goodglass, Harold, & Kaplan, 1983): Pretest reading scores on the BDAE full version subtests, i.e. B. Word Identification: 1. Word-Picture Match, and 2. Lexical Decision; C. 1. Homophone Matching; D. Derivational and Grammatical Morphology: 1. Matching to spoken sample; E. Oral Reading: 1. Basic oral word reading; F. Oral Reading of Sentences with Comprehension; and G. Reading Comprehension-Sentences and Paragraphs; will be completed prior to baseline A and initiating intervention, and immediately following completion of intervention to assess generalization to non-trained stimuli.

At three weeks follow-up the trained stimuli from all three interventions will be retested to assess retention (see Flow Diagram).

The dependent variables, i.e. differential response to the two interventions (counted as the percent correct responses per day, number of sessions required to achieve mastery at each level (simple counting), retention of the material (number of items remembered).

Reporting Participant Characteristics

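### Simultaneous presentation always precedes priming under strict alternation, so any improvement shared by both song sets biases hypotheses 3 and 4 modestly, in expectation, toward priming

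*Combined protocol and SAP*

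**What the plan says.** Section 6 (Methodology), Seventh Step, sets the sequence. At the first intervention session, with lyrics shown while the song plays, "each song (music with lyrics) from set 1 (B1 songs #1-10) will be played in its entirety". Then: "The next session, each song (music with lyrics) from set 2 (B2 songs #11-20) will be played in its entirety", with the lyrics shown afterwards (priming). After that, "The same procedures will be repeated, alternating procedures on sets 1 and 2 on subsequent treatment visits". The text gives no random start, no counterbalancing across participants and no varied order within pairs of visits. The alternation stops only at mastery, that is, it runs "until a criterion of 9/10 (90%) x 3 consecutive visits is reached on both sets". Section 4 (Study Design), whose form heading asks about randomization, describes none for session order.

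The outcomes are set in the same step and in section 7 (Data Collection). Efficiency is a tally within each procedure: "the number of sessions to criterion will be counted for each intervention". Response to the two interventions is "counted as the percent correct responses per day". Section 3 (Objectives) predicts "Simultaneous presentation will be more effective than priming with the music/lyrics" (hypothesis 3) and "Simultaneous presentation will be more efficient for facilitating recovery of reading of phrase-level material for participants with aphasia" (hypothesis 4). Section 8 (Statistical Analysis) compares these quantities with no term for order or visit number.

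**The concern.** Participants are recovering from stroke, receive speech therapy alongside the study, and repeat the same reinforced task format at every visit. Section 4 itself foresees change of this kind, since it adds a control set to detect it. Improvement common to both sets depends on calendar visit, whereas sessions to criterion are counted separately within each procedure. Because priming sits one visit further along at every session number, shared improvement is credited to it at a lower count.

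This matters because the head-to-head comparison is also read as evidence on independent versus shared processing of music and language. A systematic offset could mask a true advantage of simultaneous presentation or inflate an apparent one for priming. It is a separate matter from which songs are in which set: exchanging the sets would leave the order unchanged.

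**Working it through.** **The plan's own figures.** The plan gives no estimate of an order effect. Its visit total can be reproduced: consent 1 + pretest 1 + song testing 1 + baseline 5 + intervention 6 (three per set, the fewest that can meet the criterion) + posttest 1 + retention 1 = 16, the stated minimum. At the stated maximum of 48, about 48 − 10 = 38 visits remain for intervention.

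**Position of the sessions.** Under the written order, the k-th simultaneous session is intervention visit 2k − 1 and the k-th priming session is visit 2k.

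**Expected shift in sessions to criterion.** A set's own sessions are two visits apart, so a lead of one visit is worth 1/2 session. If a share w of the gain is common to both sets, the shift is about w × 1/2:
- w = 1: 0.5 session
- w = 0.5: 0.25 session
- w = 0.25: 0.125 session
- w = 0: none

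**Simulation with identical procedures.** The assumptions, none of them in the documents, are a 40% starting score, a rise of 2 to 5 percentage points per visit up to 97%, scores distributed Binomial(10, p), and a criterion of 9 or more on three consecutive own-set sessions. There were 40,000 simulated participants per setting. The correction and discontinuation rule was not modelled.
- All gain shared, written order: priming reaches criterion 0.48 to 0.53 session sooner on average. It is faster in about 50% of participants and simultaneous presentation in 23% to 33%; the rest tie.
- Half the gain shared: about 0.2 to 0.3 session.
- No gain shared: zero.
- The SD of the within-participant difference is about 1.6 to 2.4 sessions.
- Order randomised within pairs: the difference is zero to within about 0.03 session, and each procedure is faster equally often.

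A second parameterisation, with a rise from 40% to 97% over 6 to 30 intervention visits, gives 0.5 to 0.6 session with all gain shared, 0.24 to 0.32 with half and 0.12 to 0.16 with a quarter.

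**Percent correct.** When k-th sessions or phase means are compared, the offset is w × (gain per visit). With a rise of 97 − 40 = 57 points and w = 1:
- over 6 visits: 57/5 = 11.4 points
- over 12 visits: 57/11 = 5.2 points
- over 30 visits: 57/29 = 2.0 points

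With half shared, each figure halves.

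**The case against.** Several points against this have force.

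- **Set-specific learning.** The two procedures train different phrases, and learning specific to each set is what the study hopes to produce. If all gain were of that kind, the bias would be zero. Five baseline visits on all 30 phrases also use up some of the early task practice. This stands: the half-session figure is the upper end of the range, not the expected value, and fatigue or waning novelty would reverse the sign.
- **The control phrases.** They can show a shared trend on the same visits. However, nothing in section 8 uses them to correct the offset between the two music conditions. Section 4 places them in every third session, while the Seventh Step includes them in both session types it describes; these passages must be reconciled.
- **Plotting by visit.** On a visit axis, two identical linear trends lie on one line, so the celeration plots need not be misled. This stands for the plots, but not for counts of sessions or phase means. Also, each later simultaneous session itself follows a priming session, so the offset is a matter of matched session numbers.
- **Direction.** The bias opposes the study's own hypotheses, so a finding for simultaneous presentation would be conservative. A null finding or one for priming would not be protected.
- **The flowchart.** It might contain an order rule. The text would then still need to agree with it.

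Three stronger readings are tempting but unsupported. A reader might infer that every participant would show priming as faster, imitating replication. In the model, all four of four participants (the planned minimum) do so only about 6% of the time. A reader might also infer that each procedure becomes tied to one weekday. No visit frequency is fixed: baseline implies about 5/2 = 2.5 visits a week, and six intervention visits in two weeks would be three. Finally, a reader might extend the result to very slow gains. At 1 point per visit, mastery takes about 26 sessions per set, or 52 intervention visits, more than the 48 allowed in total.

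**Conclusion.** The concern holds as a modest, systematic bias in expectation. The written order puts priming one visit later at every matched session number, and no planned analysis removes the offset. Under the assumed model, the effect on hypothesis 4 is about 0.5 session if all gain is shared, 0.2 to 0.3 if half is, and zero if none is. For hypothesis 3 it is at most one visit's shared gain, and only where sessions are matched by number or phases are averaged. The direction toward priming rests on an upward shared trend, which is plausible here but not quantified in the documents.

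Within any one participant the effect is small beside chance variation. It does not average out, however: everyone has the same order, so neither recruiting up to ten participants nor consolidating into group means reduces it. The conclusion rests on the text of the Seventh Step, without sight of the flowchart.

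**What to change.** In section 6, Seventh Step, replace the sentence on alternation with a rule that, for each participant, the order within every consecutive pair of intervention visits (B1-B2 or B2-B1) is random and follows a list drawn before baseline. Balance the starting procedure across participants. Bring the flowchart into line. Each set still receives one session per pair.

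The cost is the pre-drawn list and one sentence; visits, materials and session content do not change. The small downside is that the same procedure can fall on two visits in a row, though never more than two.
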